7.3.2 Urinalysis

Urinalysis will be performed on Day 1 (+/- 24 hours) of all treatment cycles and at the End of Treatment visit. If protein 2+ by semi-quantitative method (eg, urine dipstick), protein will have to be quantified by 24-hour urine collection and microscopic urinalyses will have to be done (Reflex Testing). May also be performed when clinically indicated. If urine dipstick is positive for urine blood, microscopic urinalysis will have to be done (Reflex Testing), and the patient will be treated as per local standard of care based on Investigator medical judgment.

7.3.3 Electrocardiogram (ECG)

Single 12 lead ECGs will be performed at baseline, on Day 1 of Cycles 1 and 2, before avelumab infusion, and at the end of avelumab infusion. This will also be repeated at the End of Treatment visit.

If the QTc is prolonged (>500 msec, ie, CTCAE Grade 3), then the ECGs should be re-evaluated by a qualified person at the site for confirmation as soon as the finding is made, including verification that the machine reading is accurate. If manual reading verifies a QTc of >500 msec, immediate correction for reversible causes (including electrolyte abnormalities, hypoxia and concomitant medications for drugs with the potential to prolong the QTc interval) should be performed. In addition, repeat ECGs should be immediately performed hourly for at least 3 hours until the QTc interval falls below 500 msec. If QTc interval reverts to less than 500 msec, and in the judgment of the investigator(s) and Sponsor is determined to be due to cause(s) other than investigational product, treatment may be continued with regular ECG monitoring. If in that timeframe the QTc intervals rise above 500 msec the investigational product will be held until the QTc interval decreases to 500 msec. If the QTc interval has still not decreased to 500 msec after 2 weeks, or if at any time a patient has a QTc interval >515 msec or becomes symptomatic, the patient will be removed from the study.

An electronic reading of prolonged QTc must be confirmed by manual reading. Prior to concluding that an episode of prolongation of the QTc interval is due to investigational product, thorough consideration should be given to potential precipitating factors (eg, change in patient clinical condition, effect of concurrent medication, electrolyte disturbance) and possible evaluation by specialist.

7.3.4 Physical examination/clinical disease assessment

Patients will receive a physical exam, including vital signs (blood pressure, pulse, oxygen saturation, weight and height (baseline only)), and assessment of ECOG performance status on day 1 of each cycle and at the End of Treatment visit. The physical exam should also include investigation of skin lymphoma deposits and rashes, liver and spleen assessment and assessment of lymph node measurements.

7.3.5 Radiological Assessment – CT scans

A contrast enhanced CT scan of the neck, chest, abdomen and pelvis will be performed at cycles 3, 6 and 8 of treatment to assess response during treatment. If the patient discontinues treatment early an End of treatment scan should be performed, if a scan has not been conducted with the last 28 days. Scans should be reported with two dimensional measurements of each lesion in millimetres (mm) if measureable.

Immunotherapeutic agents such as avelumab may produce antitumor effects by potentiating endogenous cancer-specific immune responses. The response patterns seen with such an approach may extend beyond the typical time course of responses seen with cytotoxic agents, and can manifest as a clinical response after an initial increase (pseudo-progression) in disease burden. The Investigator's judgment of radiological response on early CT scans should be based on the overall benefit-risk assessment and the patient's clinical condition, including performance status, clinical symptoms, adverse events and laboratory data.

If the patient has not progressed after 8 cycles they will continue to be followed up with CT scans at 12, 16 and 20 months from treatment start or sooner if the investigator is concerned there may be disease progression. After 20 months from treatment start radiological follow-up will be as per local standard with data collected every 6 months.

Response will be assessed according to the Revised Response Criteria for malignant lymphoma²⁷ (appendix 1).

7.3.6 Bone Marrow Trehpene

A bone marrow trephine biopsy will be performed at screening (within 3 months of registration). If this shows involvement, the patient should undergo a further bone marrow trephine biopsy at radiological CR if this is achieved to confirm CR. Further bone marrow biopsy should also be performed if progression within the marrow is suspected and the CT does not show progression.

7.4 Research Sample Collection

7.4.1 Tumour paraffin blocks

Samples of the patient's tumour will be collected in the form of formalin-fixed paraffin embedded blocks of their initial, and relapsed or refractory diagnostic material. These samples must have been collected within 3 months of the patient registering for the trial.

In order to assay PD-L1 we will employ the VENTANA PD-L1 (SP263) kit (Roche). Results of this assay will be reviewed during the course of the trial.

Blocks will be requested immediately following registration and will be sent to the University of Leicester.

Three slides will be cut from the tissue blocks to test for PD-L1 levels.

A tissue microarray (TMA) will also be produced from diagnostic tissue block material from all patients. We will employ immunohistochemistry supported by gene expression analysis to establish a molecular classification of PTCL (see Iqbal et al.³¹) to correlate with response to treatment or predictors of relapse.

Upon relapse or progression during the study a further formalin-fixed paraffin embedded tissue block will be requested for research purposes. The collection of this tissue block is optional.

Further details will be provided in the AVAIL-T Sample collection manual.

Translational Research

Plasma and peripheral blood mononuclear cells (PBMNCs) will be collected at intervals during the study. Cell free DNA will be extracted from plasma and DNA from PBMNCs and used for analysis of the known mutations³²⁻³³ in PTCL by targeted sequencing using an IonTorrent platform. Importantly results will be correlated with PD-L1 expression levels assayed by the VENTANA PD-L1 (SP263) kit (Roche).

7.4.2 Blood samples

Blood samples will be collected at baseline, day 15 cycle 2, day 15 cycle 4, day 15 cycle 6, day 15 cycle 8, at 12 months, 16 months and 20 months post treatment start (or equivalent time point if patient is off treatment). Plasma for cell free DNA studies will be collected and peripheral blood mononuclear cells will be isolated for a CyTOF immunophenotyping sub-study.

Samples will be processed as per the AVAIL-T laboratory manual and shipped to the University of Leicester in the shipment containers supplied by the trial.

We have established droplet digital (dd) PCR assays for some of the common mutations in PTCL - RHOAG17V, IDH2 and PLCG1. We plan to employ these assays on cell free DNA from patient plasma in order to explore their utility for diagnosis and as markers for response to treatment or predictors of relapse. We estimate that one or more of these genetic markers will be detectable in 25 to 40% of our patient population^{31,34-36}.

CyTOF is a cutting-edge technology that allows the measurement of an unprecedented number of T-cell markers on circulating T-cells. We plan to perform CyTOF analysis pre-treatment and after cycles 2, 4, and 6. These data will allow the characterisation of a relapsed/refractory PTCL signature, identify putative biomarkers of response, and correlate immune cell changes with any toxicity.

For further information please see the AVAIL-T sample collection manual.

7.5 Dose Modifications

7.5.1 Infusion-Related Reactions

IRRs have been observed in patients receiving therapy with avelumab. Monitor patients for signs and symptoms of infusion-related reactions including pyrexia, chills, flushing, hypotension, dyspnoea, wheezing, back pain, abdominal pain, urticaria, rigors, diaphoresis and headache.

Table 3 outlines management guidance in the event of an IRR.

7.5.2 Severe Hypersensitivity Reactions and Flu-Like Symptoms

If hypersensitivity reaction occurs, the patient must be treated according to the best available medical practice. Patients should be instructed to report any delayed reactions to the Investigator immediately.

For prophylaxis of flu-like symptoms, 25 mg of indomethacin or comparable nonsteroidal anti-inflammatory drug (NSAID) dose (for example, ibuprofen 600 mg, naproxen sodium 500 mg) may be administered 2 hours before and 8 hours after the start of each dose of avelumab IV infusion. Alternative treatments for fever (for example, paracetamol) may be given to patients at the discretion of the Investigator.

Table 3. Treatment Modification for Symptoms of Infusion-Related Reactions

NCI-CTCAE Grade	Examples of Qualifying events (NCI CTCAE)	Treatment Modification for Study Drug
Grade 1 – mild Mild transient reaction; infusion interruption not indicated; intervention not indicated.	Transient hypotension; palpitations; mild hypertension; mild allergic reaction (transient rash, drug fever <38°C), other mild reactions: flushing, rigor, chills, pruritus, cough, pain, nausea, vomiting.	Decrease the study drug infusion rate by 50% and monitor closely for any worsening.
Grade 2 – moderate Therapy or infusion interruption indicated but responds promptly to symptomatic treatment (for example, antihistamines, NSAIDs, narcotics, IV fluids); prophylactic medications indicated for ≤ 24 h.	Hypotension requiring fluid replacement; advanced hypertension or symptomatic arrhythmias not requiring treatment; moderate allergic reaction (urticaria, drug fever >38°C) or isolated fever 39.1 to 40°C; severe &/or prolonged rigors/chills; frequent or drenching diaphoresis; controlled or intense or widespread pruritis; cough requiring narcotic antitussive; other moderate reactions: pain, GI, skin, etc	Temporarily discontinue study drug infusion. Resume infusion at 50% of previous rate once infusion-related reaction has resolved or decreased to at least Grade 1 in severity, and monitor closely for any worsening. If a Grade 2 infusion-related reaction does not improve or worsens following implementation of the modifications indicated above (including reducing the infusion rate by 50%), treatment should be commenced based on the specific symptoms and the infusion should not be resumed for that cycle. At the next cycle, consider the addition of an H2-blocker, meperidine, or ibuprofen to the mandatory premedication.
Recurrent Grade 2 – moderate		In the event of further recurrence, in spite of implementation of all measures indicated above, (including reducing the infusion rate by 50%), hydrocortisone 100 mg IV may be added to the premedication schema outlined above following discussion with the trials office.
Grade 3 – severe Grade 3: Prolonged (for example, not rapidly responsive to symptomatic medication and/or brief interruption of infusion); recurrence of symptoms following initial improvement; hospitalisation indicated for clinical sequelae.	Angina, congestive heart failure, hypotension, hypertension or arrhythmias requiring medication, moderate allergic reaction) severe allergic reaction (symptomatic bronchospasm requiring parenteral medications, with or without urticaria, allergy-related edema/angioedema), fever >40°C for <24 hrs, rigors/chills unresponsive to	Stop the study drug infusion immediately and disconnect infusion tubing from the subject. If IV fluids to maintain blood pressure, or prolonged administration of steroids, or inotropic agents, or administration of oxygen to maintain peripheral saturations are required, or the symptoms persist for more than 48 hours: 
 • Permanently discontinue avelumab treatment If none of the conditions listed above applies,

	
narcotics; uncontrolled intense or widespread pruritus, uncontrolled severe cough; dyspnoea at normal activity; other severe pain, GI or skin symptoms, etc.
 
Or Acute myocardial infarction, tamponade, hypertensive crisis, life-threatening arrhythmia, shock, anaphylaxis, renal failure, fever $>40^{\circ}\text{C}$ for >24 hrs, other life-threatening or disabling reactions.
	
 consider resuming avelumab treatment if the risk/benefit assessment for the individual patient is positive and agreed with the trials office/CI if the decision is made to resume treatment, the infusion rate must be reduced by 50% AND hydrocortisone 200 mg IV must be added to the standard premedication. 
Stop the study drug infusion immediately and disconnect infusion tubing from the subject.
 
Subjects have to be withdrawn immediately from study drug treatment and must not receive any further study drug treatment.


Recurrent Grade 3 – severe
 
Grade 4 – life-threatening
 
Grade 4: Life-threatening consequences; urgent intervention indicated.
		
Stop the study drug infusion immediately and disconnect infusion tubing from the subject.
 
Subjects have to be withdrawn immediately from study drug treatment and must not receive any further study drug treatment.

In addition, if premedication with hydrocortisone is necessary it should be added for at least the subsequent 2 cycles of avelumab treatment.
		

IV = intravenous; NCI-CTCAE = National Cancer Institute-Common Terminology Criteria for Adverse Event; NSAIDs = nonsteroidal anti-inflammatory drugs.

[figure not shown]

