12.1.2 Secondary outcome measures

- Toxicity assessed using CTCAE v4.0 will be defined as the number and proportion of patients who experience one or more grade 3 or 4 adverse event or serious adverse event of any grade
- Best overall response (Partial Remission (PR) + Complete Response (CR)) at any time of treatment will be assessed using contrast-enhanced CT scans of the neck, chest, abdomen and pelvis, using the Revised Response Criteria for Malignant Lymphoma (²⁷)
- Maximum percentage change in the sum of the product of diameters (SPD) of target tumour masses assessed by contrast-enhanced CT scans of the neck, chest, abdomen and pelvis, using the Revised Response Criteria for Malignant Lymphoma²⁷
- Duration of response is defined as the time from first documented response until relapse/progression, as determined by the Revised Response Criteria²⁷, or death. Patients who are relapse/progression free and alive will be censored at date last seen.
- Progression free survival is defined as the time from date of registration to the date of disease progression or date of death from any cause. Patients not reaching progression or death at the time of analysis will be censored at the last date they were known to be alive and progression free. Patients will be followed up for a minimum of 12 months.
- Overall survival time is defined as the time from date of registration to the date of death from any cause. Patients discontinuing the study, lost to follow-up or still alive at the end of the study will be censored at the date of last follow-up. Patients will be followed up for a minimum of 12 months.

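### Table 3 lists moderate allergic reaction under both Grade 2 and Grade 3, and the two rows give different instructions that part completely on recurrence

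*Combined protocol and SAP*

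**What the plan says.** Table 3 has three columns: the NCI-CTCAE grade with its definition, examples of qualifying events, and the treatment modification.

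**Grade 2.** The definition reads "Therapy or infusion interruption indicated but responds promptly to symptomatic treatment (for example, antihistamines, NSAIDs, narcotics, IV fluids". The examples include "Hypotension requiring fluid replacement" and "moderate allergic reaction (urticaria, drug fever >38°C) or isolated fever 39.1 to 40°C". The instruction is to interrupt and then: "Resume infusion at 50% of previous rate once infusion-related reaction has resolved or decreased to at least Grade 1 in severity". For recurrent Grade 2 reactions the table adds an optional premedication step after discussion with the trials office. It does not require withdrawal.

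**Grade 3.** The definition is a prolonged reaction (for instance one that does not respond quickly), a return of symptoms after first improving, or a need for hospital admission. The examples include "hypertension or arrhythmias requiring medication, moderate allergic reaction) severe allergic reaction (symptomatic bronchospasm requiring parenteral medications". The instruction is to stop at once and disconnect. A list of conditions, opening "If IV fluids to maintain blood pressure, or prolonged administration of steroids, or inotropic agents", leads to permanent discontinuation. If none of them applies, resumption may be considered if the trials office or Chief Investigator agrees, at half rate and with mandatory hydrocortisone. A recurrent Grade 3 reaction requires withdrawal from study drug.

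**Table 5 (section 7.8)** exempts a first Grade 3 infusion reaction from discontinuation only if it meets the Table 3 conditions. It also sends recurrent Grade 2 infusion reactions back to Table 3.

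**The concern.** A site that grades by matching the patient to the examples column can place the same moderate allergic reaction in either row. At the first reaction this changes three things: whether the infusion is paused or disconnected, whether central agreement is needed before resuming, and which premedication is required. At the second reaction the rows give incompatible outcomes, since one lets the patient stay on avelumab and the other withdraws the patient. Two sites could therefore handle the same patient differently while both follow the table. A patient withdrawn in this way loses whatever remains of the 16 doses planned over 8 cycles.

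**Working it through.** This is a comparison of text. No sample size, probability or error rate in the plan depends on it.

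**Step 1: set the two rows side by side.**

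| | Read as Grade 2 | Read as Grade 3 |
|---|---|---|
| Moderate allergic reaction in the examples | Yes, with its own illustrations | Yes, with no illustrations and an unmatched bracket |
| Definition column | Prompt response to treatment | Prolonged, recurring after improvement, or needing admission |
| First reaction | Pause, resume at half rate | Stop and disconnect; resume only if no listed condition applies and with central agreement |
| Recurrent reaction | May continue | Withdraw |
| Table 5 | Refers to Table 3 | Refers to Table 3 |

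The Grade 2 cell already holds a complete entry for this event. The Grade 3 mention is therefore a duplicate, and not text displaced from the Grade 2 cell.

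**Step 2: apply the table to one patient.** Take urticaria with drug fever above 38°C that settles promptly when the infusion is paused. The definition column gives Grade 2. The examples column matches both rows. If the same reaction returns at a later infusion, the Grade 2 reading permits continuation and the Grade 3 reading requires withdrawal. Table 5 gives no independent answer, because it refers to Table 3 for both grades.

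**Step 3: check the IV-fluids wording.** Fluids appear in the Grade 2 definition and examples, and again in the Grade 3 action cell. In the Grade 3 row they are a condition applied after a reaction has been graded 3. They do not define Grade 3. Hypotension corrected promptly with fluids is thus Grade 2 by the definition column. The boundary is blurred, but the two entries do not directly contradict each other.

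**Step 4: scale.** Section 1.2.3 reports infusion reactions in 49 of 480 patients: 49/480 = 10.2%, as stated there. Assuming that rate applies here:

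- expected patients with any reaction, N = 30: 30 × 49/480 = 3.06
- expected patients with any reaction, N = 35: 35 × 49/480 = 3.57
- chance of at least one, N = 30: 1 − (431/480)^30 = 0.960

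These counts cover all grades. Section 1.2.3 says most reactions were Grade 1 or 2, and no figure gives the share near the Grade 2/3 boundary. The counts are therefore an upper limit on the number of patients affected.

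**The case against.** The strongest reply is that the table already resolves the matter. Its second column is headed as examples, the definition sits in the grade column, and section 8.2.1.1 requires CTCAE v4.0 grading. The Grade 3 entry, with its stray bracket directly before severe allergic reaction, looks like leftover text. A first Grade 3 reaction may also resume at half rate, as Grade 2 does. Much of this stands: a careful reader would grade by the definition. But the table does not say so, the duplicate remains in the operative text, and the possibility of resuming under Grade 3 ends at recurrence.

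A reader might infer more than the documents support in four ways.

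- **That IV fluids produce a direct conflict between resuming and permanent stopping.** They do not. The fluids condition applies only within Grade 3, and the grades are separated by promptness of response.
- **That the toxicity outcome is directly distorted.** Section 12.1.2 counts the "number and proportion of patients who experience one or more grade 3 or 4 adverse event", together with patients who have a serious event of any grade, and grading is by CTCAE v4.0. Table 3 labels itself with CTCAE grades, so a site could carry its grade to the AE form, but that link is indirect.
- **That the primary result is weakened.** Appendix 2 shows the probability of a response rate above 35% falling from 74% with 12 of 30 responses to 60% with 11. Any single lost responder gives that change, so it does not measure this defect.
- **That every event should appear in one grade only.** Hypotension and rigors or chills recur across grades with different qualifiers, and that is not an error.

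The 49/480 rate may also not carry over. Section 1.2.3 says premedication was mandated after two serious reactions were reported in that experience, whereas section 7.1 here requires it for the first four doses.

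**Conclusion.** The point holds in a narrow form. Moderate allergic reaction appears in both the Grade 2 and the Grade 3 examples of Table 3, the rows carry different instructions, and on recurrence the instructions are incompatible. Table 5 does not resolve this. The IV-fluids wording is a secondary matter of clarity.

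The number of patients affected is likely to be small. At the section 1.2.3 rate, about 3 to 4 of 30 to 35 patients would have any infusion reaction, and only some of those would be moderate allergic reactions. That figure assumes the solid-tumour rate transfers. The conclusion does not depend on it, because it rests on the wording of the table alone. The point deserves correction because the table governs whether a patient continues treatment. No view is taken here on which row is clinically right.

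**What to change.** Reconcile the Grade 2 and Grade 3 rows of Table 3 so that moderate allergic reaction leads to a single instruction. The clinical team decides the content.

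Add one sentence stating that the grade-definition column, with CTCAE, decides the grade when it and the examples disagree. The column headings and section 8.2.1.1 already point that way.

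In the same edit, make clear that the Grade 3 condition on IV fluids applies only to reactions already graded 3 by the definition column, since hypotension needing fluids is a Grade 2 example.

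The cost is a wording correction in the next amendment and a note to sites. It needs no extra visits, tests or patients, and no change to the statistical analysis.

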7.5.3 Tumour Lysis Syndrome

There is a potential risk of tumor lysis syndrome (TLS) because avelumab can induce antibody-dependent cell-mediated cytotoxicity. Patients should be monitored closely via standard blood tests and if there is a clinical suspicion of TLS it should be managed according to best medical practice. Management of TLS may include aggressive hydration, monitoring of renal function, correction of electrolyte abnormalities, anti-hyperuricaemic therapy, and supportive care.

Should this occur, patients should be treated per the local guidelines or the management algorithm below (Figure 1)

Figure 1

Assessment and initial management of tumour lysis syndrome.

